6.3 Long Term Treatment Period

All subjects will enter the long term treatment period after Week 2, although dose adjustment may continue in Switch subjects and titration may continue in Rollover subjects.

During long term treatment, all subjects will be contacted by telephone at Week 3 and will return to the clinic on Weeks 4, 8, 15, 28 and every 13 weeks thereafter for evaluation of safety and chorea control. In addition, Rollover subjects will have an additional telephone contact at Week 5. Switch subjects will have an additional telephone contact at Week 7, to remind subjects to complete diary card before the Week 8 visit. **Subjects who have not achieved a dose level that adequately controls chorea and is well tolerated by the Week 4 visit (Switch subjects) or Week 5 telecon (Rollover subjects) should have unscheduled visits or telephone contacts in order to further adjust their dose upward or downward.** Site interactions for dose adjustment should alternate between telephone contacts and clinic visits. During long-term treatment, further dose adjustments of SD-809 ER may be made, if necessary, but not more often than weekly and in increments of 6 mg (6 mg/day or 12 mg/day after a total daily dose of 48 mg is reached). Dose adjustments should be based on all available information including the subject's and caregiver's reports of adverse events and chorea control, information from rating scales and all safety evaluations. If subjects become non-ambulatory or require more aid than an assistive device during long term treatment, they will be permitted to remain in the study.

At the end of the long term treatment period, subjects will undergo a comprehensive evaluation, including physical and complete neurological exam, safety labs and 12-lead ECG and performance of all rating scales.

6.3.1 Telephone Contacts (One week prior to Baseline visit [Switch only]; Week 3 ± 3 days [All Subjects]; Week 5 ± 3 days [Rollover only]; Week 7±3 days [Switch only])

See the Schedule of Events A and B for a detailed summary of activities.

All subjects will be contacted by telephone during Week 3 to assess adverse events, chorea control (in consultation with the subject and caregiver), concomitant medication use, evaluation of study drug dose level and adjustment, if necessary and to schedule/confirm the next visit. Following the above assessments, study medication will be re-ordered according to specified procedures.

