8.3 Safety Analyses

Safety and tolerability will be assessed throughout the study by monitoring the following parameters:

 • Adverse events (AEs) • Clinical laboratory tests • Physical examination • Vital signs • 12- lead ECGs • Epworth Sleepiness Scale (ESS) 	
 • Columbia Suicide Severity Rating Scale (C-SSRS) • Unified Huntington’s Disease Rating Scale (UHDRS) • Swallowing Disturbance Questionnaire (SDQ) • Unified Parkinson’s Disease Rating Scale (UPDRS), dysarthria item • Barnes Akathisia Rating Scale (BARS) • Hospital Anxiety and Depression Scale (HADS) • Montreal Cognitive Assessment (MoCA©)
---	--

Safety data will be summarized descriptively for the overall population and based on prior treatment [SD-809 ER or placebo (Rollover subjects) or tetrabenazine (Switch subjects)]. Descriptive statistics will be calculated for quantitative data and frequency counts and percentages will be provided for categorical data. Descriptive statistics of change-from-baseline for Rollover subjects will utilize the Baseline from Study SD-809-C-15 (C-15 Baseline) and the Baseline from the present study (C-16 Baseline), as appropriate, and will be specified in the Statistical Analysis Plan.

The nature, frequency, and severity of adverse events will be tabulated for all subjects combined and by treatment. Baseline, within study, end of study, and change-from-baseline values for clinical laboratory evaluations and vital signs will be summarized as appropriate.

Treatment-emergent adverse events and laboratory, vital sign, and ECG parameters will be summarized. In addition, change from baseline will be summarized for laboratory and vital sign parameters. Shift tables will be provided for clinical laboratory results. ECG results will be classified as normal and abnormal and summarized.

8.4 *Safety Endpoints*

The following safety endpoints will be assessed:

- Incidence of adverse events (AEs), serious AEs, severe AEs, drug related AEs, AEs leading to withdrawal during the following periods:
 - Overall
 - During titration in Rollover subjects (up to 8 weeks)
 - During dose adjustment in Switch subjects (up to 4 weeks)
 - During long term treatment
- Observed values and changes from baseline in clinical laboratory parameters (hematology, chemistry, and urinalysis)
- Observed values and changes from baseline in vital signs
- Observed values in ECG parameters and abnormal findings

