8.9 Analysis Visit Windows

For efficacy and safety by-visit analyses, data collected at post baseline scheduled visits will be included using their nominal visit. Data collected at early termination, end of treatment, and unscheduled visits will be assigned to a visit window as described below. All scheduled visits will be assigned a target study day; for the determination of target days, weeks will be assumed to have 7 days. Thus, Week 4 would have a target day of $4 \times 7 = 28$ days. For each visit, a visit window will be assigned so that anything from the midpoint to the prior target day to the midpoint to the following target day will be assigned to that visit window as shown in Table 3 below. The following rules concerning visit windows and selecting records for analysis will be used:

1. Scheduled visit has precedence.

2. If there are multiple records of the same scheduled visit, the record closest to the target day will be used for analysis. If two records are equidistant, then the earlier one will be used.
3. For a given visit, if there is no data from a scheduled visit, data from an unscheduled visit that occurs in the visit window will be used for analysis.

Table 3: Analysis Visit Window

| Visit | Target Day | Visit Window |
|-----------------------------|------------|--------------|
| Screening | -5 | (--, -5) |
| Screening Telephone Contact | -2 | (-4, -2) |
| Baseline | -1 | (-1, -1) |
| Week 1 | 7 | (1,10) |
| Week 2 | 14 | (11-17) |
| Week 3 | 21 | (18, 24) |
| Week 4 | 28 | (25, 31) |
| Week 5 | 35 | (32, 38) |
| Week 7 | 49 | (39, 52) |
| Week 8 | 56 | (53, 80) |
| Week 15 | 105 | (81, 150) |
| Week 28 | 196 | (151, 241) |
| Week 41 | 287 | (242, 332) |
| Week 54 | 378 | (333, 423) |
| Week 67 | 469 | (424, 514) |
| Week 80 | 560 | (515, 605) |
| Week 93 | 651 | (606, 697) |
| Week 106 | 742 | (698, 787) |
| Week 119 | 833 | (788, 879) |
| Week 132 | 924 | (880, 970) |
| Week 145 | 1015 | (971, 1060) |
| Week 158 | 1106 | (1061, 1152) |
| Week 171 | 1197 | (1153, --) |

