9.9.3 Orthostatic Vital Signs

Orthostatic blood pressure and heart rate will be recorded at Baseline and Week 8. The Baseline and Week 8 differences between supine and standing systolic and diastolic blood pressure and heart rate, and the change from Baseline to Week 8 in these differences will be summarized using descriptive statistics.

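### End-of-treatment and early-termination values can be displaced by an older scheduled value in the same analysis window, and the SAP plans no end-of-treatment summary

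*SAP*

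**What the plan says.** SAP 8.9 keeps scheduled post-baseline visits under their nominal week but handles other records differently: "Data collected at early termination, end of treatment, and unscheduled visits will be assigned to a visit window as described below". The windows are defined as follows: "anything from the midpoint to the prior target day to the midpoint to the following target day will be assigned to that visit window". Table 3 has 20 post-baseline rows, from Week 1 to an open-ended Week 171. The first selection rule is "Scheduled visit has precedence". The third applies row by row: "if there is no data from a scheduled visit, data from an unscheduled visit that occurs in the visit window will be used for analysis".

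Neither Table 3 nor SAP 9.7 to 9.9 defines an EOT, ET or last on-treatment row. SAP 8.5.2 excludes imputation of missing endpoints, so no carry-forward brings a displaced value back.

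Protocol 6.3 states: "At the end of the long term treatment period, subjects will undergo a comprehensive evaluation". Protocol 6.3.3 asks for the same assessments at ET. Protocol 8.3 states: "Baseline, within study, end of study, and change-from-baseline values for clinical laboratory evaluations and vital signs will be summarized as appropriate". SAP 8.10, which records departures from the protocol's analyses, does not mention dropping the end-of-study part.

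For orthostatic measurements, Protocol 6.6.5 and SAP 9.9.2 both include EOT/ET as a collection point. SAP 9.9.3 says "Orthostatic blood pressure and heart rate will be recorded at Baseline and Week 8" and summarizes only those two visits.

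**The concern.** Treatment runs until US commercial availability, so its length differs between subjects and later calendar rows hold only those still in the study. Results at the point of leaving drug would normally be read from an end-of-treatment row, and this plan has none. The EOT/ET visit carries one of the fullest evaluations after baseline. When its record is displaced, the table shows a value up to about 45 days older. For a subject who stops because of an adverse event or poor chorea control, that gap is where a change could appear, and a reader would have to find it in the listings.

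Two related gaps follow. The end-of-study summary foreseen in Protocol 8.3 disappears without being recorded as a change. SAP 8.9 also sets no limit on time since the last dose. Protocol 6.3.3 takes the ET pharmacokinetic sample only within 48 hours of the last dose, so later ET visits are anticipated, and their off-drug values would be windowed with on-drug ones.

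**Working it through.** **Inputs.** Target days, windows and selection rules: SAP 8.9 and Table 3. Assessment schedules: the schedules of events, Protocol 6.3.2 and SAP 9.9.6.

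**Reproducing a printed window.** Lower bound = floor((previous target + target)/2) + 1. Upper bound = floor((target + next target)/2). For Week 54: floor((287 + 378)/2) + 1 = 333 and floor((378 + 469)/2) = 423, as printed. The rule also matches Weeks 1-4 and 8-80. From the upper bound of Week 93 onward the printed bounds differ by at most one day. The Week 5/Week 7 boundary is printed as 38/39 where the rule gives 42/43. None of this changes the result materially.

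**One 13-week interval.** Suppose the Week 54 visit takes place on day 378. An EOT record on days 379-423 falls in the Week 54 window, which already holds a scheduled record, and is displaced. On days 424-469 it falls in the empty Week 67 window and is used. Displaced: 45 of 91 days = 49.5%. In four intervals (starting at Weeks 93, 119, 132 and 158) the printed bounds give 46/91 = 50.5%.

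**Days 197-1197.** These are 11 intervals × 91 = 1001 days. For each schedule, count the days after a scheduled record of that assessment up to the end of its window, taking EOT day as uniform and visits on target:

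| Assessment | Scheduled at (from Week 28) | Displaced days | Share |
|---|---|---|---|
| TMC, total motor score, HADS, BARS, ESS, SDQ, UPDRS speech, MoCA, UHDRS cognitive and behavior, vital signs, weight | every 13 weeks | 7×45 + 4×46 = 499 | 49.9% |
| Labs, schedule of events | 28, 54, 80, 106, 132, 158 | 4×45 + 2×46 = 272 | 27.2% |
| Labs, SAP 9.9.6 (adds Week 41) | as above plus 41 | 272 + 45 = 317 | 31.7% |
| TFC | 28, 80, 132 | 2×45 + 46 = 136 | 13.6% |
| Functional Assessment, Independence, Clinical Summary | 28 only | 45 | 4.5% (0% after day 241) |

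Letting visits vary by ±3 days moved these shares by no more than 0.1 percentage point.

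**Other intervals, every-visit assessments.** Weeks 8-15: 24/49 = 49.0%. Weeks 15-28: 45/91 = 49.5%. Weeks 4-8: days 29-31, 3/28 = 10.7%. Switch, Weeks 1-4: days 8-10, 3/21 = 14.3%. Rollover, Weeks 2-4: days 15-17, 3/14 = 21.4%. Early shares are small because windows for telephone contacts hold no scheduled scales. After an attended Week 171 visit the open-ended window displaces any later EOT record of these assessments.

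**Sensitivity to timing.** If every EOT falls within 45 days of the last visit, the loss is 100%. If EOT takes the place of the next 13-week visit, it is 0%.

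**Scatter.** After day 241, EOT values for Functional Assessment, Independence and Clinical Summary are kept but spread over 11 rows (Weeks 41 to 171). As an illustration, 36 planned Switch subjects spread evenly would give 36/11, or about 3 per row.

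**Reading of the third rule.** It names unscheduled visits only. The counts assume it also covers EOT/ET, because the section groups them together. Without that inference the loss is larger.

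**The case against.** The best defense is that nearest-visit windowing is a prespecified choice in a single-arm, descriptive study with no formal testing (SAP 8.1), and that all eCRF data are listed (SAP 8.7). This stands, and so do several limits on what may be inferred:

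- A reader might infer that half of last on-drug values vanish from every by-visit table. The schedules do not support that. The figure applies only to every-visit assessments and rests on an assumed stopping pattern.
- A reader might infer that displacement turns later rows into summaries of survivors. It does not. A displaced record belongs to the row of a visit the subject completed, and the subject still contributes that value. Later rows contain only continuing subjects under any rule, and an ET record that is not displaced adds a stopper to the next row.
- EOT is not a long-term value that every subject has. Some stop in the first weeks, and ET assessments are to be done if possible (Protocol 6.14).
- Protocol 8.3 covers laboratory and vital-sign values, with a qualifier, and Protocol 8 leaves details to the SAP. It makes no such commitment for TMC or the rating scales.
- The four-day threshold in SAP 8.7 selects an off-treatment baseline for Rollover subjects. It does not define on-treatment values and gives no ground for discarding late ET records, which may come from subjects who stopped for adverse events.
- The orthostatic omission comes from SAP 9.9.3, not from the precedence rule.

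The defense does not answer the absence of any tabulated end-of-treatment result, or the silence of SAP 8.10 on the end-of-study summaries.

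**Conclusion.** The point holds in limited form. EOT/ET records yield to an older scheduled record in the same window, and no end-of-treatment row is planned. Displacement is about half for every-visit assessments, 27-32% for labs, 14% for TFC and 0-5% for Functional Assessment, Independence and Clinical Summary. All these shares assume uniform stopping dates over days 197-1197, visits near target, and EOT/ET treated like unscheduled records. The documents give no stopping-date distribution, and for every-visit assessments the share can lie anywhere from 0 to 100%. What is lost from the table is the latest record, not the subject. Adverse event analyses and C-SSRS counts at any post-baseline time are unaffected. The gap does not threaten the study's main safety tables, but it is worth closing in a long-term study of variable length.

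**What to change.** Add to SAP 8.9 a row named *End of Treatment/ET (last on-treatment value)* that a scheduled visit never displaces. Report it with change from baseline for TMC, total motor score, the rating scales, labs (with shift tables), weight, vital signs and the supine-to-standing differences of SAP 9.9.3. Prespecify how many days after the last dose a value may still be called on-treatment. Flag later ET values or show them separately rather than dropping them. State in the third selection rule whether it covers EOT/ET records.

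The cost is SAP wording and one extra row per table. No new data are needed, because Protocol 6.3.3 already collects these assessments.

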6.5 Unscheduled Visit(s)

See the Schedule of Events A and B for a detailed summary of activities.

Unscheduled visits may be performed for Dose Adjustment or evaluation of intercurrent events. Visits for Dose adjustment should focus on evaluating chorea control, adverse events

and adjusting the dose of study medication, if indicated. Additional safety measures may be performed at the investigator's discretion.

For unscheduled clinic visit(s) conducted during the course of the study, the following activities should be performed:

- Assessment of adverse events, chorea control (in consultation with the subject and caregiver), and concomitant medications
- Vital signs and weight
- Unified Huntington's Disease Rating Scale (UHDRS)
 - Motor
- Evaluation of study drug dose level and adjustment, if necessary

The following assessments are at the Investigator's discretion and should be performed if indicated:

- 12-lead ECG
- Clinical laboratory tests: serum chemistry, hematology, and urinalysis
- Single PK Blood Sample (for Unscheduled Visits due to SAE, if within 48 hours, if possible)
- Hospital Anxiety and Depression Scale (HADS)
- Columbia Suicide Severity Rating Scale (C-SSRS): Since Last Visit version
- Unified Parkinson's Disease Rating Scale (UPDRS): dysarthria item
- Barnes Akathisia Rating Scale (BARS)
- Epworth Sleepiness Scale (ESS)
- Swallowing Disturbance Questionnaire (SDQ)

- Re-order study medication

For unscheduled telephone visit(s) needed during the course of the study, the following activities should be performed:

- Assessment of adverse events, chorea control and concomitant medications in consultation with the subject and caregiver.
- Evaluation of study drug dose level and adjustment, if necessary (at the Investigator's discretion)

- Re-order study medication (at the Investigator's discretion) (See Operations Manual for further details)

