9.9.2 Vital Signs and Weight

Respiration rate (breaths/minute), temperature (°C), and weight (kg) will be obtained at each clinic visit. Supine and standing systolic and diastolic blood pressure (mmHg) and supine and standing heart rate (beats/minute) will be collected at the Baseline, Week 8, and End-of-Treatment/Early Termination visits. Seated blood pressure and heart rate will be collected at all other visits.

Weight, respiration rate, temperature, seated/supine systolic and diastolic blood pressure, and seated/supine heart rate, and the corresponding change from baseline, will each be summarized by visit using descriptive statistics.

A listing of weight and vital sign assessments will also be provided.

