9.9.6 Clinical Laboratory Assessments

Serum chemistry, hematology, and urinalysis laboratory tests will be performed at Screening (Switch subjects only), Baseline (Switch subjects only), Week 8, Week 28, Week 41, Week 54, and every 26 weeks thereafter. For Rollover subjects, the screening assessment will be prior data from study SD-809-C-15. Laboratory parameters that will be assessed include the following:

Table 4: Clinical Laboratory Tests

| Serum Chemistry | | |
|--|---|---|
| 
 • Sodium • Potassium • Chloride • Bicarbonate • Magnesium • Glucose • Blood urea nitrogen (BUN) | 
 • Creatinine • Total calcium • Phosphate • Uric Acid • Cholesterol • Triglycerides • Total Protein | 
 • Albumin • Total bilirubin • Direct bilirubin • Alkaline phosphatase (ALP) • Alanine aminotransferase (ALT) • Aspartate transaminase (AST) • Lactate dehydrogenase (LDH) |
| Hematology | Urinalysis | |
| 
 • Hemoglobin • Hematocrit • Red blood cell count (RBC) • Mean cell volume (MCV) • Platelets • White cell count • Neutrophils • Lymphocytes • Monocytes • Eosinophils • Basophils | 
 • Leucocytes • Nitrites • Urobilinogen • Protein • pH • Blood • Specific gravity • Ketone • Bilirubin • Glucose • Microscopic exam (if indicated) | |
| Screening Labs | | Other |
| 
 • Urine and serum pregnancy tests (women of childbearing potential only) • Follicle Stimulating Hormone (FSH) for post-menopausal women only. • Hepatitis B surface antigen (HBsAg) | | 
 • CYP2D6 genotype (blinded) • CAG repeat • Prothrombin Time |

Serum chemistry and hematology results and changes from screening/baseline will be summarized at each visit using descriptive statistics. In addition, all serum chemistry and hematology results will be categorized into the following categories using the laboratory reference ranges: below lower limit of normal, normal, above upper limit of normal. Shift tables summarizing changes in status from screening/baseline to each post-baseline visit will be presented. All laboratory results including urinalysis results will be listed.

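### Abnormal unscheduled laboratory, vital-sign and weight readings are left out of the safety tables whenever the same visit window holds a scheduled test, and no worst on-treatment summary picks them up

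*SAP*

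**What the plan says.** SAP 8.9 applies the same rules to efficacy and safety: "For efficacy and safety by-visit analyses, data collected at post baseline scheduled visits will be included using their nominal visit". Data from early termination, end of treatment and unscheduled visits are placed in the Table 3 windows. Three rules then choose the record.

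- Rule 1: "Scheduled visit has precedence".
- Rule 2: "If there are multiple records of the same scheduled visit, the record closest to the target day will be used for analysis". On ties, "If two records are equidistant, then the earlier one will be used".
- Rule 3 begins "For a given visit, if there is no data from a scheduled visit, data from an unscheduled visit that occurs in the visit window" and provides that such data are then used.

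The measured value plays no part in the choice.

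The safety tables that depend on this choice are by visit. SAP 9.9.2 says that weight and vital signs and their changes from baseline "will each be summarized by visit using descriptive statistics". SAP 9.9.6 gives chemistry and hematology by visit and adds: "Shift tables summarizing changes in status from screening/baseline to each post-baseline visit will be presented". Neither section plans a worst-value, any-post-baseline or threshold table. Urinalysis is listed only.

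Protocol 6.5 provides for unscheduled visits for dose adjustment or intercurrent events. Vital signs and weight are required at each unscheduled clinic visit. Laboratory tests are left to the investigator's "discretion and should be performed if indicated".

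**The concern.** Safety is the main purpose of this study, and laboratory values and vital signs are named safety endpoints (Protocol 8.4, SAP 7.2). Some unscheduled readings are taken because something happened to the subject between visits. For by-visit means, keeping these readings out is reasonable, because it stops irregular measurements from distorting a visit average. For describing the extremes reached on treatment it is not, because a rule based on scheduling decides whether an abnormal value is counted.

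The SAP takes an any-time approach elsewhere. C-SSRS outcomes are counted at any post-baseline time point (9.9.7), and QTcF above 450 msec at any visit defines a subset (9.9.5). Laboratory tests and vital signs have no equivalent. With about 36 Switch and 80 Rollover subjects planned, one subject missing from an abnormal category is 1/36 = 2.8 or 1/80 = 1.25 percentage points of a cohort.

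**Working it through.** The plan states no figure on this point, so the check applies the rules to cases and counts the days on which they bite.

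**Inputs.** Rules 1-3 and Table 3 (SAP 8.9). Visit window of ±3 days for Week 4 onward (Protocol 6.3.2). Laboratory schedule: Weeks 8 and 28, then every 26 weeks (Protocol 6.3.2), or Weeks 8, 28, 41 and 54, then every 26 weeks (SAP 9.9.6). Vital signs and weight at every scheduled clinic visit (Schedules of Events A and B).

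**Rules applied to cases**

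| Records | Target day | Record used |
|---|---|---|
| Scheduled normal Day 56; unscheduled abnormal Day 70 | 56 | Normal; abnormal is dropped |
| Scheduled abnormal Day 54; unscheduled normal Day 56 | 56 | Abnormal |
| Unscheduled abnormal laboratory test Day 100, no scheduled draw at Week 15 | 105 | Abnormal (rule 3) |
| Both recorded as Week 8: abnormal Day 53, normal Day 56 | 56 | Normal; abnormal is dropped |
| Both recorded as Week 8: abnormal Day 56, normal Day 59 | 56 | Abnormal |
| Both recorded as Week 8: abnormal Day 54, normal Day 58 | 56 | Abnormal (tie, earlier kept) |

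**Vital signs and weight.** From Day 53 (start of the Week 8 window) every Table 3 window belongs to a clinic visit with scheduled vital signs. For a subject attending all visits, rule 3 then never applies. Before Day 53, the windows without scheduled vital signs are:

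- Switch: Days 11-24 and 32-52, 14 + 21 = 35 days.
- Rollover: Days 1-10, 18-24 and 32-52, 10 + 7 + 21 = 38 days.

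Over Days 1-1152, windows with scheduled vital signs cover 1152 − 35 = 1117 days (97%) for Switch and 1152 − 38 = 1114 days (97%) for Rollover.

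**Laboratory tests.** Windows with a scheduled draw up to Day 1152 (the last Table 3 window is open-ended and is left out):

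- Protocol schedule, Weeks 8, 28, 54, 80, 106, 132 and 158: 28 + 91 + 91 + 91 + 90 + 91 + 92 = 574; 574/1152 = 50%.
- SAP schedule, which adds Week 41 (91 days): 574 + 91 = 665; 665/1152 = 58%.

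In the remaining 50% or 42% of days an unscheduled laboratory value can enter the by-visit table.

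**Retest recorded under the same scheduled visit (assumption).** Let x be the day of the original relative to target, from −3 to +3, and g the gap in days to the retest. The retest replaces the original only if |x + g| < |x|.

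- g = 1: x = −3, −2, −1
- g = 2 or 3: x = −3, −2
- g = 4 or 5: x = −3
- g = 6 or more: never

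The original must therefore precede the target day and the retest must follow within 5 days.

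**Effect on extremes.** The by-visit tables show minimum and maximum (SAP 8.7), but over selected records. A maximum over a subset cannot exceed the maximum over all records, and a minimum cannot fall below it. The tabulated extremes can understate the on-treatment range and cannot overstate it.

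**The case against.** The strongest reply is that 8.9 often protects an abnormal result. A scheduled abnormal value cannot be displaced by a retest recorded as unscheduled. Post-baseline, Protocol 6.5 routes extra tests to unscheduled visits, and the only stated provision for repeating laboratory tests concerns screening. This stands. A reader might infer that normal retests routinely overwrite the abnormal results that prompted them. The documents do not support that, because nothing says a post-baseline redraw is filed under the scheduled visit.

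Second, abnormal values have other outlets. A selected abnormal value enters the by-visit statistics and, for chemistry and hematology, the shift table. All results are listed (SAP 8.7, 9.9.6). Abnormalities meeting the definition in Protocol 7.1.1 become adverse events, and those arising on treatment are tabulated under SAP 9.9.1. The Clinical Monitor reviews aggregate laboratory data and alert values monthly (Protocol 9.4.2). All of this is correct, so it would be wrong to conclude that worst values reach no table. It does not close the gap. Listings give no counts or shifts, adverse-event tables give events rather than values, and not every abnormal reading meets the definition.

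Third, the rules ignore the value, and unscheduled visits also serve dose adjustment, so a general bias toward normal is not shown. That stands for visit means. The one-sided effect on extremes remains.

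Fourth, the protocol promises observed values, changes from baseline and laboratory shift tables, and the SAP supplies them without formal testing. True, so this is an improvement to the plan and not a breach of the protocol.

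**Conclusion.** The concern holds in a limited form. An abnormal unscheduled laboratory, vital-sign or weight reading that shares a window with a scheduled test is absent from every laboratory and vital-sign table. It survives in listings and, where it qualifies, as an adverse event.

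For vital signs and weight this covers every window from Day 53, assuming the subject attends all visits. For laboratory tests it covers 50% or 58% of Days 1-1152, depending on which schedule is followed. These are shares of calendar days on which a reading could be left out. They are not shares of abnormal readings lost, which the documents do not allow anyone to estimate. The long gap between scheduled draws late in the study is a matter of sampling frequency and is no evidence about 8.9.

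Replacement by a retest is a secondary route. It rests on the unstated recording convention and on the narrow timing shown in the working. The loss of unscheduled readings does not depend on it and is enough to justify a cheap change.

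**What to change.** Keep rules 1-3 of SAP 8.9 for by-visit summaries and say that they apply to those only. In 9.9.2 and 9.9.6 add, for each parameter, the highest and the lowest on-treatment value per subject from first to last SD-809 dose, taken over all scheduled, repeat, unscheduled and early-termination records. Summarize these with change from baseline for vital signs and weight, and with shift from baseline for laboratory tests, using the baseline in SAP 8.7. State whether an early-termination sample drawn just after the last dose counts as on treatment.

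In 8.9, also say how a post-baseline retest is labelled, which record is used when several unscheduled readings share a window, and how early-termination and end-of-treatment records rank under rules 1-3.

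The cost is SAP wording and a few extra table rows, with no new data. The downside is that these rows include for-cause readings and will look less favourable than visit means, so the table title should say which records are included.
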